6.3.1 Pharmacokinetics Analysis

Plasma Fesomersen-eq. concentrations and dialysate concentrations of Fesomersen and its metabolites, respectively, will be summarized by visit and planned sampling time intervals, separated according to actual dose cohort. Descriptive statistics [geometric mean and percent coefficient of variation (%CV), arithmetic mean and %CV, median and range] will be presented by treatment group and time in tabular form. Analysis comparing regular and alternative PK sampling group will be done. Means at any time will only be calculated if at least 2/3 of the individual data were measured and were above the lower limit of quantification (LLOQ). For the calculation of the mean value, a data point below LLOQ will be substituted by one half of this limit. In tables showing mean values, where values below LLOQ are included in the calculation of mean values, these means will be marked.

Box-plots for Fesomersen-eq. trough (C_{trough}) plasma concentrations will be provided by actual dose cohort and visit.

For all treatments where at least one subject with at least one confirmed ADA formation is included, the individual concentrations of Fesomersen in plasma will be displayed including supplemental information about the ADA titer. Individual subjects with confirmed ADA formation will be indicated by different colors and symbols.

Pharmacokinetic and exposure-response analysis using population approaches (popPK and popPK/PD, e.g., by non-linear mixed effect modeling) will be reported under separate document, if applicable.

6.3.2 Pharmacodynamic Analysis

Analysis comparing regular and alternative PD sampling will be done.

6.3.2.1 The PD profile

The effect of Fesomersen on PD profile will be assessed on maximum change in FXI activity levels, FXI antigen levels, PT, INR, aPTT, d-dimer, TAT, and F1.2 levels during the main treatment period by treatment group in PD analysis set.

Change and percent change from baseline FXI activity levels, FXI antigen levels, PT, INR, aPTT, d-dimer, TAT, and F1.2 levels will be summarized by treatment and visit separately. Individual results will be presented in data listings by treatment. Figures of the mean levels of all PD parameters (FXI activity and antigen, PT, INR, aPTT, d-dimer, TAT and F1.2) as well as change and percent change from baseline will be provided by treatment group, and scheduled visit.

Change and percent change from baseline in FXI activity levels, FXI antigen levels, PT, INR, and aPTT will be compared between each of the study intervention group and pooled placebo group using the Wilcoxon Rank Sum test.

Frequency and percent of patients with average FXI activity $\leq 0.1, \leq 0.2, \leq 0.3, ..., \leq 1.0 \text{ U/mL}$ during each visit with PK/PD measurements up to last dose + 28 days will also be provided.

The incidence and events for any aPTT>160s will be summarized by treatment and visit.

For all treatments where at least one subject with at least one confirmed ADA formation is included, the PD parameters. in plasma will be displayed including supplemental information about the ADA titer. Individual subjects with confirmed ADA formation will be indicated by different colors and symbols.

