All cohorts will consist of 1-week screening period and a 24-week main treatment period, the last 4 weeks of which are an evaluation period for certain PD and safety parameters. To collect additional long-term safety information, participants will continue to be treated as randomized in the extended treatment period, with up to 24 weeks of additional treatment with study intervention. A participant is considered to be on treatment until 4 weeks after their last dose, whether they discontinue treatment early, complete only the main treatment period, or complete part or all of the extended treatment period. Once the overall treatment period is completed, participants will have a 16-week post-treatment follow-up period.

07 JUL 2021 Page: 30 of 90

All participants who are in the extended treatment period will need to stop further treatment no later than when the last participant enrolled into the study has completed the 24-week main treatment period (Visit 22). Participants in the extended treatment period will complete Visit 28 four weeks after their last dose, and move to the 16-week post-treatment follow-up period. The sponsor reserves the discretion to halt further dosing in the extended treatment period earlier in anticipation of the least participant completing the main treatment period.

The data and outcomes collected in the study will be analyzed by 4 groups:

- Pooled Placebo Group (from Cohorts A, B and C),
- 40 mg Dose Group (BAY 2976217 from Cohort A),
- 80 mg Dose Group (BAY 2976217 from Cohort B), and
- 120 mg Dose Group (BAY 2976217 from Cohort C).

All suspected bleeding, cardiovascular and thromboembolic events occurring after randomization will be assessed by CIAC blinded to treatment allocation. An independent DMC will monitor the participant's safety and give recommendations to the Steering Committee.

The DMC will review unblinded data from the study on regular basis, as outlined in the DMC Charter. At any time, if there is an unexpected finding(s) in Cohort C (the 120 mg dose cohort), the DMC may elect to modify the Cohort C to a 100 mg or 80 mg dose level. If recommended by the DMC, the change will be implemented by administrative letter and will not require a protocol amendment. All ongoing participants will have their dosing modified to 100 mg or 80 mg once monthly and all new participants will be initiate dosing at 100 mg or 80 mg once monthly.

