that the 200 mg regimen was noninferior, and the 300 mg regimen of FXI-ASO was superior to enoxaparin. These data would support the investigation of a higher FXI suppression level of approximate 20% remaining FXI activity.

Spontaneous bleeding, including clinically significant bleedings, do not show dependency on lower levels of FXI in the above cited publications and other published literature. In addition, no increase in number of clinically significant bleeding under treatment with the parent compound BAY 2306001 was seen in two studies with ESRD patients.

With a view on potential clinical efficacy and considering safety, reduced FXI levels of less than 15% to approximately 50% remaining activity are justified for the current study. The three doses of 40 mg, 80 mg, and 120 mg BAY 2976217 have been selected to optimally cover for this range.

A protocol-defined option for dose step-down for the 120 mg dose level (see section 4.1) is provided to the DMC. Also, the predicted steady-state FXI levels with 120 mg once monthly dosing are expected to be similar to those achieved with the 300 mg dose level in the TKA study (ISIS 416858-CS3) in which no increased clinically significant bleeding was observed.

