8.5.1 Sampling time for PK, PD and immunogenicity

Table 8-1: Overview PK/PD and immunogenicity, sampling

	Main treatment p	eriod																			
Sampling	Туре	V1	V2 ^a	V3 ^a	V4 ^a	V5	V6	V7	V8	V9	V10	V11	V12	V13	V14	V16	V18	V19	V20	V21	V22
Plasma PD	At any time	•	•	•	•																
Plasma PK/PD	pre-dose (trough)					•					•		•		•	•	•				● _p
	3-4 h post administration ^c					•					•										
	5-6 h post administration d					•					•										
	22-32 h post administration						•														
	At any time during the visit							•	•	•		•		•				•	•	•	● _p
Dialysate PK	15 min to 30 min after the start of dialysis					•	(•) ^e				•										
	30 min to 0 min prior to the end of dialysis					•	(•) ^e				•										
Immunogenicity	Pre-dose					●f					•				•						● _p
	At any time								•												
	Extension treatment and Follow-up period																				
		V23	V24	V25	V26	V27	V28	FU1	FU4	ET											
Plasma PK/PD	pre-dose (trough)	•	•	•	•	•															
PK/PD	Any time during the visit						•	•	•	•											
Immunogenicity	Pre-dose		•		•																
	At any time						•		•	•										•	

ET = early termination visit, min = minute(s), h = hour(s), PD = Pharmacodynamic(s), PK = Pharmacokinetic(s)

a Visits 2, 3 and 4 are only applicable before implementation of amendment 1, for patients enrolled as of amendment 1 these visits are not performed.

b At Visit 22, plasma PK and PD, and immunogenicity sampling will be done before dosing (trough sample) if the participant receives study intervention. In cases when the participant does not receive study intervention at Visit 22, sampling can occur at any time during the visit.

c 3-4 hour PK sample should be taken very close to the 3 hour timepoint if possible.

d If routine care procedures are incompatible with the 5-6 hour time window, the sample may be taken earlier but not before 4 1/2 hours after study drug administration.

e Samples will be collected on V6 for patients in alternative PK&PD sampling group, as they will have dialysis on V6.

f At V5 Immunogenicity sample will be drawn pre-hemodialysis, before the first dose of study intervention.

07 JUL 2021 Page: 58 of 90

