8.5.1.1 PK, PD and immunogenicity sampling (all participants)

- Visit 5 will be conducted on a dialysis day. The first dose of study intervention will be administered on Visit 5, prior to the start of the dialysis session. Visit 5 plasma PK/PD samples will be drawn at timepoints described in Table 8–1. Dialysate effluent will be collected 15 minutes to 30 minutes after the start of dialysis, and during the final 30 minutes of dialysis. Visit 5 immunogenicity sample will be drawn pre-HD, before the first dose of study intervention.
- Visit 6 will be conducted the day after Visit 5, on a non-dialysis day. The Visit 6 plasma PK/PD sample will be drawn 22-32 hours after the first dose of Study intervention administration on Visit 5.
- Visit 10 will be conducted on a dialysis day. Dosing on Visit 10 will occur prior to the start of the dialysis session. Visit 10 plasma PK/PD samples will be drawn at timepoints described in Table 8–1. Dialysate effluent will be collected at 15 min to 30 min after the start of dialysis and during the final 30 minutes of dialysis. The total dialysis volume should be recorded.
- At Visit 12, Visit 14, Visit 16, Visit 18 (main treatment period) and Visits 23-27 (extended treatment period) plasma PK and PD, and immunogenicity (when applicable) sampling will be done before dosing (trough sample), at other visits sampling can occur at any time during the visit.
- At Visit 22, plasma PK and PD, and immunogenicity sampling will be done before dosing (trough sample) if the participant receives study intervention. In cases when the participant does not receive study intervention at Visit 22, sampling can occur at any time during the visit.

8.5.1.2 PK, PD and immunogenicity sampling, participants from the alternative PK&PD sampling group starting on a non-dialysis day

- For these participants, study intervention will be administered on a non-dialysis day preceding a scheduled dialysis day.
- Visit 5 will be conducted on a non-dialysis day preceding a scheduled dialysis day. The first dose of study intervention will be administered on Visit 5. Visit 5 plasma PK/PD samples will be drawn at timepoints described in Table 8–1. Immunogenicity samples will be drawn before the first dose of study intervention on Visit 5.
- Visit 6 will be conducted the day after Visit 5, on a dialysis day. The Visit 6 plasma
 PK/PD sample will be drawn 22-32 hours after the first study intervention

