9.4.5 Pharmacodynamic endpoints

The PD profile will be assessed as described in Section 8.6.

• Changes in FXI antigen levels and FXI activity levels:

Maximum change in FXI activity and antigen levels during the main treatment period will be summarized by treatment groups.

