As there is currently no accepted alternative therapy to reduce thrombotic events in this population except the use of low-dose ASA, the appropriate standard of care for the control arm of each cohort is placebo with or without low-dose ASA at the discretion of the investigator.

This statistical analysis plan (SAP) is based on the Global Clinical Study Protocol BAY 2976217/21170 version 3.0 dated 07 JUL 2021 and contains definitions of analysis sets, key derived variables and statistical methods for the LICA study. It provides a technical and detailed elaboration of the principal features of the planned analyses, e.g., derivation of the primary endpoints. Amendments and/or appendices to this core SAP may be used to add additional analysis and provide more details on the coding guidelines, data-handling, and output tables and figures.

Titles, mock-ups, and programming instructions for all statistical output (tables, figures, and listings (TLF)) are provided in a separate TLF specifications document.

2. Study Objectives

Objectives and endpoints are listed in Table 2-1.

Table 2-1: Objectives and Endpoints

Objectives	Estimands/Endpoints
Primary	
• To evaluate the safety of Fesomersen as compared to placebo	 Primary Endpoint The incidence of major bleeding and clinically relevant non-major bleeding during the main treatment period and within the on-treatment time window, as assessed by blinded CIAC
Secondary	
To evaluate the safety of Fesomersen as compared to placebo	 The incidence of the composite of major bleeding and clinically-relevant non-major bleeding during the main and extended treatment periods and within the on-treatment time window, as assessed by blinded CIAC Incidence and severity of TEAEs during the main treatment period and within the on-treatment time window the main and extended treatment periods and within the on-treatment time window the main and extended treatment periods and within the on-treatment time window the main and extended treatment periods and within the on-treatment time window the main and extended treatment periods and until 20 weeks after the last study intervention dose
• To evaluate the PK and PD of Fesomersen	 Pharmacokinetic Endpoints Trough concentrations for 3 dose levels of Fesomersen Pharmacodynamic Endpoints Maximum change in FXI antigen levels during the main treatment period Maximum change in FXI activity levels during the main treatment period
Exploratory	

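### The named FXI secondary endpoint is a peak-effect statistic with an incomplete definition; no estimate of sustained FXI suppression against placebo with a confidence interval is pre-specified

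*SAP*

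**What the plan says.** SAP Table 2-1 lists the FXI secondary endpoints as maximum change in antigen and in activity, for example "Maximum change in FXI activity levels during the main treatment period". SAP 6.3.2.1 carries this into the analysis: "The effect of Fesomersen on PD profile will be assessed on maximum change in FXI activity levels, FXI antigen levels". Protocol 9.4.5 agrees: "Maximum change in FXI activity and antigen levels during the main treatment period will be summarized by treatment groups". Neither document says whether the maximum is the largest fall or the largest change in either direction, or whether it is absolute or percent.

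The SAP baseline (6.1.3) is one value, the latest available before the first dose; values are averaged only when a timepoint has repeats.

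SAP Table 5-2 gives maximum FXI change the OA data scope. SAP 4.5.2 runs that scope to the end of post-treatment follow-up, which does not match the main treatment period in the endpoint text.

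Protocol 4.1 describes the 24-week main period as one "the last 4 weeks of which are an evaluation period for certain PD and safety parameters". Protocol 9.4.6.3, in its text on the clotting score and PD biomarkers, says a mean over V19-V22 can be formed. The SAP does not carry this over for FXI.

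SAP 6.3.2.1 also plans change and percent change by visit, mean-level figures, Wilcoxon comparisons with placebo on change and percent change, and counts of participants by average FXI activity category.

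**The concern.** A maximum over repeated noisy samples is an order statistic. Even with no drug effect, the lowest of many values tends to fall below a single baseline value, and the more samples a participant has, the lower it tends to be. The result mixes drug effect with assay and biological noise and with length of follow-up. About 15% are expected to drop out, so sample counts will differ between participants.

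The doses were justified by a range of FXI levels: "reduced FXI levels of less than 15% to approximately 50% remaining activity are justified for the current study" (Protocol 4.3). The natural question for each dose is the level it holds. The named endpoint answers a different question, the lowest level reached. What is at stake is how the secondary FXI figure per dose will be read, and whether the plan contains one pre-specified, placebo-adjusted estimate of sustained suppression with its uncertainty. It does not.

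**Working it through.** The plan gives no FXI figure to reproduce: no SD, no expected change and no sizing on FXI.

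**Number of samples** (Protocol Table 8-1 and 8.5.1.1; V5 pre-dose is baseline):
- Trough: V10, V12, V14, V16, V18, V22 = 6. The text reads "At Visit 12, Visit 14, Visit 16, Visit 18 (main treatment period) and Visits 23-27"; V10 and V22 come from the table, and V22 is counted once.
- 3-4 h at V5 and V10 = 2; 5-6 h at V5 and V10 = 2.
- "22-32 h post administration" at V6 = 1.
- "At any time during the visit": V7, V8, V9, V11, V13, V19, V20, V21 = 8.
- Total 6 + 2 + 2 + 1 + 8 = 19 for a completer.
- Under the OA scope, FU1 and FU4 make it 21 without extension. V23-V28 as well make it 27.

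**Noise-only fall, by hand.** The expected minimum of 19 independent standard normals is -1.844. With lognormal noise, s = sqrt(ln(1 + CV²)) and the expected log ratio of lowest value to baseline is -1.844 × s. At CV 10%, s = 0.0998, the log ratio is -0.184, and exp(-0.184) - 1 = -16.8% on the geometric scale.

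**Simulation.** 200,000 participants, independent lognormal noise on baseline and on every sample. On active dose, FXI declines over the first 7 samples and is at target for the last 12. The CV is an assumption. Mean of the largest percent fall:

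| Assumed CV | Placebo (true 0) | 50% remaining (true -50) | 20% remaining (true -80) | Placebo, 5 samples only |
|---|---|---|---|---|
| 5% | -9 | -54 | -82 | -6 |
| 10% | -16 | -57 | -83 | -10 |
| 15% | -23 | -60 | -84 | -15 |
| 20% | -29 | -63 | -85 | -18 |

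**Difference from placebo, same model.** For the 50% dose: 54 - 9 = 45, 57 - 16 = 41, 60 - 23 = 37 and 63 - 29 = 34 points, against a true 50. For the 20% dose at CV 10%: 83 - 16 = 67, against a true 80. The gap between the two doses at CV 10% is 83 - 57 = 26 points, against a true 30.

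**Sensitivity to the noise model.**
- Correlation of 0.6 at 7 days: the placebo fall at CV 10% is -14.4%.
- Normal noise proportional to level, all 19 samples at target, change in points of baseline: placebo -9 to -37 over SD 5% to 20% if independent, and -8 to -33 with correlation 0.6.
- Constant additive noise, SD 10 points, all 19 at target: placebo -18.5 and the 50% dose -68.5. The difference is 50.0, so the bias cancels (ignoring the floor at zero).
- Largest absolute change with its sign (normal model, SD 10%): the placebo mean is about 0, half the participants are positive, and the average size is 27 points.

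**Evaluation-period mean.** In the normal model the V19-V22 mean gives 0.0 to -0.1 points on placebo and returns about -50 and -80 for the two doses. In the lognormal model the geometric mean also returns the true levels.

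**The case against.** The strongest reply is that the plan already shows sustained levels. By-visit change and percent change include V19-V22. Mean-level figures by visit and the average-FXI categories are not extremes over time, and PK/PD modelling is to be reported separately. The lowest FXI reached is also a legitimate quantity in a safety study whose primary endpoint is bleeding. All of this stands, and it limits the consequence. But none of these outputs is a single pre-specified estimate of sustained suppression against placebo with a confidence interval. The SAP does plan one for the exploratory clotting score (6.3.2.2), as mean differences from placebo with 90% and 95% intervals.

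Four stronger readings are tempting and should be resisted:
- A reader might infer that the inflated figure will choose the Phase 3 dose. Protocol 4.1 ties dose selection to the primary analysis as a whole and names no FXI criterion.
- A reader might infer that the drug effect is exaggerated. That is true only within an arm. Against placebo the effect is understated or about right.
- A reader might infer that a placebo reduction is certain and large. It needs the largest-fall reading, which is natural for an FXI-lowering drug but unwritten, and its size rests on an assumed CV.
- A reader might infer that the Wilcoxon tests use raw change only. They cover percent change too, although no interval estimate is specified with them.

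The overstatement is also small at deep suppression: 3 points for the 20% dose at CV 10%.

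**Conclusion.** The point holds as one of definition and completeness. The named FXI endpoint, read as the largest fall, is a peak-effect statistic whose expectation depends on noise and sample count. Over an assumed CV of 5% to 20% with independent lognormal noise, the within-arm overstatement is about 4 to 13 points for a dose holding 50% and 2 to 5 points for one holding 20%; placebo shows 9 to 29 points with no true change. The placebo contrast errs the other way under proportional noise and is roughly unbiased under additive noise. These sizes rest on the assumed CV, on a completer's full 19 samples and on the direction of the maximum, none of which the documents guarantee. Two defects need no assumption: the endpoint's direction and scale are undefined, and Table 5-2 assigns it a scope that contradicts its own text. This is a worthwhile, low-cost correction. It does not invalidate the planned FXI reporting.

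**What to change.** 1. In SAP 6.3.2.1, define maximum change (direction; absolute or percent), label it as peak effect, and always show it beside pooled placebo.
2. In SAP Table 5-2, replace the OA scope for maximum FXI change so that it matches the main treatment period. Otherwise the number of samples (up to 27) varies with each participant's extension length.
3. Add, for FXI activity and antigen, the geometric mean of the V19-V22 values. Analyse it by ANCOVA on the log scale with log baseline, treatment, ASA use and CV-risk stratum. Report ratio to baseline per dose and ratio to placebo, each with a 95% CI. State that the SAP 6.1.3 baseline applies, since Protocol 9.4.6.3 still describes a screening-week mean. Give the number of participants contributing, because early leavers will lack these visits.

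The cost is SAP wording and one table; no new samples are needed. The within-arm figure per dose becomes slightly less favourable.

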6.3.2.2 SQCS Analysis

The effect of Fesomersen on the clotting in the dialysis circuit will be assessed by the SQCS.

The clotting assessment will be conducted on the PD analysis set and will be presented according to treatment group. Clotting scores will be assigned as follows:

Clotting score	Definition
Clotting Score 0	Clean filter and no visible clots in the drip chambers
Clotting Score 1	For traces of coagulation in the filter and/or in the drip chambers
Clotting Score 2	Intermediate state between 1 and 3
Clotting Score 3	Fully clotted extracorporal system resulting in an interruption of the
	hemodialysis session

Table 6-1: Clotting scale score

Adequate anticoagulation is defined by an SQCS of less or equal "1".

The summary of each clotting score category will be presented in frequency and the percentage of patients by visits.

The overall score for individual subjects, which is the highest clotting score from all visits per data scope, will also be summarized. The overall clotting score will be analyzed for treatment comparison between each Fesomersen dose groups and placebo group using the Wilcoxon Rank Sum test.

The difference in the mean of SQCSs during the main treatment period between each of the Fesomersen groups and the placebo group will be displayed together with the corresponding 90% (and 95%) confidence intervals applying ANOVA with treatment group as factor.

Furthermore, the difference in the proportion of hemodialysis sessions with adequate anticoagulation during the main treatment period between each of the Fesomersen dose groups and the placebo group will be summarized with the corresponding 90% (and 95%) confidence intervals using the unstratified exact method with the standardized test statistic and inverting a two-sided test (Agresti and Min, 2000) as exploratory analysis.

Frequency of dialyzer filters usage will be analyzed through descriptive statistics.

Most severe clotting category

In order to examine the correlation of FXI activity level and clotting, a separate summary on the most severe clotting category will be provided for patients with average FXI activity ≤ 0.1 , ≤ 0.2 , ≤ 0.3 , ..., ≤ 1.0 U/mL for Fesomersen treated patients only.

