At the end of the hemodialysis procedure, at specified time points, the filter and line (including drip chamber/air trap) will be examined by the hemodialysis nurse (or respective appropriate personnel) after rinsing the circuit. Clotting scores will be assigned as follows:

- "0" clean filter and no visible clots in the drip chamber/air trap
- "1" traces of coagulation in the filter and/or in the drip chamber/air trap
- "2" intermediate state between "1" and "3"
- "3" fully clotted extracorporeal system resulting in an interruption of the hemodialysis session

Adequate anticoagulation is defined by a SQCS of less or equal "1".

Overall score is the highest of the individual component scores:

Inspection Site	Category 0	Category 1	Category 2	Category 3
Drip chamber (also referred to as air trap)	No visible clots in the drip chamber	Trace (e.g fibrinous ring with no clot formation on venous chamber)	Intermediate (e.g clot formation on venous chamber, more than "1" but not fully clotted)	Fully clotted system (treatment cannot continue without new setup)
Dialyzer	Clean dialyzer	Trace (e.g blood stripes affecting less than approximately 5% of the fibers seen at the surface of the dialyzer)	Intermediate (e.g blood stripes affecting approximately 5% or more of the fibers seen at the surface of the dialyzer, but not fully clotted)	Fully clotted filter

Only one (highest) score will be documented in the eCRF.

The clotting score will be recorded as specified in the SoA. The dialyzer and drip chamber/air trap will be assessed for clotting score at the end of the dialysis session on the visit day (or from a dialysis session within the visit window if the visit is not conducted on a dialysis day).

For information on PD sampling see Section 8.5.

The study sponsors reserve the right not to conduct all or part of the above-mentioned analysis.

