9.4.6.3 Pre-specified PD endpoints

• Changes in PT, INR, and aPTT:

Maximum change in PT, INR, and aPTT levels during the main treatment period will be summarized by treatment group.

• Extent and frequency of clotting on the dialysis filters & circuit:

The extent and occurrence of clotting on the dialysis filters and circuit will be summarized descriptively by category scoring (SQCS) as described in Section 8.6. For a change from baseline to evaluation period analysis, the baseline for liver enzymes, platelets, PD biomarkers including the clotting score, AV access bleeding score will be the mean of measurements taken during the 1-week screening period. The final 4 weeks (Visits 19-22) would be the evaluation period from which a mean value can be determined from measurements taken during this period.

• Changes in d-dimers:

Change and percent change in d-dimers will be tabulated by treatment group by study visit.

- TAT
- F1.2

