This is a Phase 2 multicenter, double-blind, randomized, placebo-controlled study in ESRD patients who are stable on HD (including hemodiafiltration) \geq 3 months for a minimum of 9 hours per week. Patients receiving therapeutic anticoagulation or antiplatelet therapy (other than ASA \leq 150 mg/day) are excluded. Approximately 288 participants will be randomized. Participants will be allocated at randomization to 1 of 3 dose cohorts in a 1:1:1 ratio (Cohort A [40 mg], Cohort B [80 mg], and Cohort C [120 mg]), and within each cohort to receive SC treatment with either Fesomersen or matching placebo in a 3:1 ratio. Sponsor, participants and investigators are blinded with respect to active treatment versus matching placebo, but assignment to dose cohort will be known. The CIAC will be blinded to dose cohort allocation and treatment assignment. With an assumed attrition rate of 15% during the main treatment period, 288 randomized participants would allow for an estimated 240 evaluable participants.

All standard of care hemodialysis therapies as prescribed by their providers, including use of heparins to maintain dialysis circuit patency, will be continued.

- Cohort A: 40 mg Fesomersen or placebo SC (3:1) n~96
- Cohort B: 80 mg Fesomersen or placebo SC (3:1) n~96
- Cohort C: 120 mg Fesomersen or placebo SC (3:1) n~96

Participants will be stratified at randomization for use of ASA (yes/no). The use of ASA will remain at the discretion of the investigator. However, all efforts should be made during the treatment period to avoid change in ASA use or dose, unless clinically indicated. Additionally, participants will also be stratified based on the presence of selected CV risk factors. The investigator will evaluate the presence or absence of the following at the time of randomization:

- (i) age >65 years,
- (ii) history of DM type I or II,
- (iii) history of MI,
- (iv) history of stroke or TIA,
- (v) history of CHF,
- (vi) history of PAD,
- (vii) history of Afib.
- Strata 1 zero or one risk factor, except the presence of DM or Afib; .

Strata 2 - either DM or Afib alone, or two or more risk factors.

All cohorts will consist of a 1-week screening period and a 24-week main treatment period (visit 5 to visit 22), the last 4 weeks of which are an evaluation period for certain PD and safety parameters.

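### The SAP's clotting-score comparisons omit the baseline-to-Visit 19-22 analysis described in the protocol, leave the collected baseline score unused, and count the first-dose session as on-treatment

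*SAP*

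**What the plan says.** Protocol 9.4.6.3 first says that clotting will be summarised descriptively by SQCS category. It then describes a change from baseline to an evaluation period. For this the baseline of "PD biomarkers including the clotting score, AV access bleeding score will be the mean of measurements taken during the 1-week screening period", and "The final 4 weeks (Visits 19-22) would be the evaluation period from which a mean value can be determined". SAP section 3 keeps the idea of an evaluation period: "24-week main treatment period (visit 5 to visit 22), the last 4 weeks of which are an evaluation period".

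SAP 6.3.2.2 gives category frequencies by visit and three treatment comparisons:

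- a participant-level overall score, "which is the highest clotting score from all visits per data scope", compared by Wilcoxon rank sum test;
- "The difference in the mean of SQCSs during the main treatment period", with 90% and 95% intervals, "applying ANOVA with treatment group as factor";
- the proportion of sessions with adequate anticoagulation in the main treatment period, by an unstratified exact method.

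None of the three uses a baseline score or isolates Visits 19-22. SAP 6.3.2.1 does compare change from baseline between groups for FXI activity, FXI antigen, PT, INR and aPTT. The change history in SAP section 7 does not mention the difference for SQCS.

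**The concern.** Less clotting of the dialysis circuit is the finding the protocol cites from the parent compound in haemodialysis patients, and protocol 4.1 says the primary analysis is meant to expedite Phase 3 dose selection. The SQCS contrasts will therefore be read alongside the FXI data, exploratory or not.

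Three features work against a clear reading:

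- The main treatment period starts at the first dose (SAP 4.5.1), so it takes in a score recorded before any material effect is plausible.
- The Visit 1 score is collected but not used to reduce between-patient variation.
- The highest score over all visits can only rise as more visits are attended, so it partly reflects time in the study.

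**Working it through.** **Planning figures.** The documents give no effect size, standard deviation, correlation or power for SQCS, so there is no SQCS figure to reproduce. The relevant planning number is 60 completers per group. From 72 per group at 15% dropout, 72 × 0.85 = 61.2, which agrees.

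**Which scores enter the mean.** In the schedule of activities (protocol 1.3), clotting is scored at V1 and then at V5, V8, V10, V12, V14, V16, V18, V19, V20, V21 and V22. That is 11 main-period scores, counting V22 by date. Seven precede Visits 19-22. On a dialysis day the dose is given within 15 minutes of the start of dialysis (protocol 6.1), and the score is taken at the end of the session (protocol 8.6.2). The V5 score is therefore post-dose by hours: it is neither a baseline nor a useful on-treatment value.

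**Dilution from the schedule alone.** If every visit except V5 carries the full effect, the whole-period difference is 10/11 = 0.909 of the Visit 19-22 difference, or about 9% smaller.

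**Dilution with gradual onset (assumed).** Let the effect at t days after the first dose be 1 − 2^(−t/h), with t = 0, 14, 28, 56, 84, 112, 140, 147, 154, 161, 168. The ratio is the mean over all 11 visits divided by the mean over the last four. Dropping V5 multiplies it by 11/10.

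| Onset half-life h (days) | Ratio with V5 | Ratio without V5 |
|---|---|---|
| 7 | 0.880 | 0.968 |
| 14 | 0.834 | 0.917 |
| 21 | 0.795 | 0.875 |
| 28 | 0.765 | 0.842 |
| 42 | 0.725 | 0.797 |

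Shrinkage with V5 included is thus 12% to 27.5%.

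**Variance.** Assume unit variance and equal correlation r between visits. The mean of k scores has variance V(k) = (1 + (k − 1)r)/k. Adjusting for one baseline score removes r², a fraction r²/V(k).

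| r | V(4) | V(11) | V(11) below V(4) by | Baseline cut, V19-V22 mean | Baseline cut, 10-visit mean (no V5) | Signal-to-noise, 11-visit vs V19-V22, both unadjusted, only V5 null |
|---|---|---|---|---|---|---|
| 0.2 | 0.400 | 0.273 | 32% | 10% | 14% | 1.10 |
| 0.3 | 0.475 | 0.364 | 23% | 19% | 24% | 1.04 |
| 0.5 | 0.625 | 0.545 | 13% | 40% | 45% | 0.97 |
| 0.7 | 0.775 | 0.727 | 6% | 63% | 67% | 0.94 |

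The last column is (10/11)/√(V(11)/V(4)). With the gradual-onset ratios instead of 10/11, it runs from 0.75 (h = 42, r = 0.7) to 1.07 (h = 7, r = 0.2).

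**Simulation (illustrative).** Settings: ordinal 0-3 score, 60 per group, assumed latent shift 0.4 SD, two-sided 10% level, h = 14 to 28 days, latent correlation 0.3 to 0.5.

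| Analysis | Power |
|---|---|
| SAP whole-period ANOVA | 67-87% |
| SAP worst-ever score, Wilcoxon | 53-67% |
| V19-V22 mean, unadjusted | 80-88% |
| V19-V22 mean, ANCOVA | 90-92% |
| Whole period without V5, ANCOVA | 89-96% |
| V19-V22 simple change from baseline | 55-65% |

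In this simulation both baseline-adjusted means do well whichever window is used, whereas a plain change score does worse than the SAP's ANOVA.

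**Worst-ever score.** Assume a 10% chance of a score of 2 or more at each visit, independent between visits. The chance of at least one is 1 − 0.9^11 = 69% with 11 visits and 1 − 0.9^6 = 47% with 6. The measure depends on visits attended even when the per-visit risk is the same.

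**The case against.** The other side has a good deal right.

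- **Permissive protocol text.** The firm statement in 9.4.6.3 is the descriptive category summary, and the SAP keeps that by visit, so Visits 19-22 are shown. The evaluation-period sentences are conditional and may be leftover text: Visits 2-4 are no longer performed, and Amendment 2 gave up averaged baselines. A reader might infer that the SAP overrides a binding pre-specified analysis; the wording does not support that. What stands is that the protocol names the clotting score in this analysis and the SAP neither includes it nor explains its absence.
- **Averaging more visits reduces noise.** A reader might infer that the whole-period mean is noisier. It is not: its variance is 6% to 32% lower than that of the four-visit mean at r = 0.7 to 0.2. This offsets much of the dilution.
- **Early effect.** One might also treat V8 (day 15) as carrying no effect, giving 9/11 or 18% dilution. The documents give no time course for FXI or SQCS in this population, and they present slow loading as a drawback of the unconjugated parent. Only V5 follows from the schedule.
- **Overall score.** Protocol 8.6.2 says "Overall score is the highest of the individual component scores", meaning drip chamber and dialyzer within one session. The SAP takes the maximum of those session scores per participant. The two share a label; session scoring has not been redefined.
- **Retention.** Fewer visits bias the worst-score comparison only if retention differs by arm, which is not shown. A Visit 19-22 window has its own retention problem: under protocol 7.1.1, participants who stop treatment in the main period go to Visit 22 four weeks after the last dose and can lack Visits 19-21.
- **Status.** SQCS is exploratory, and protocol 8.6.2 lets the sponsor omit it. Calling it the trial's main marker of clinical effect has no source in the documents.

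**Conclusion.** The point holds in limited form. The protocol describes a screening-to-Visit 19-22 comparison for the clotting score, and the SAP contains none and gives no reason.

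The certain cost to the whole-period mean is about 9% dilution from V5, taking full effect at every later visit. The 12% to 27.5% range rests on assumed onset half-lives of 7 to 42 days and is partly offset by averaging more scores. The clearer loss is the unused Visit 1 score: about 10% to 63% of the variance of the Visit 19-22 mean, at assumed visit correlations of 0.2 to 0.7. Because allocation is randomised, leaving out the covariate costs precision and does not bias the comparison.

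It would be wrong to conclude that the SAP's SQCS comparisons are invalid or that the Visit 19-22 mean should displace them. The primary safety analysis is unaffected.

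**What to change.** Change SAP 6.3.2.2 as follows:

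1. Replace the treatment-only ANOVA of the whole-period mean with an ANCOVA that includes the pre-dose Visit 1 score as covariate. Do not use a simple change score.
2. State that V5 counts neither as baseline nor as on-treatment, and exclude it from the on-treatment mean and the worst-score summary.
3. Add the Visit 19-22 mean with the same ANCOVA, alongside the whole-period analysis. State a rule for early discontinuers, for example the mean of their last available on-treatment scores.
4. Keep the worst-ever comparison as supportive, and give the participant-level maximum a different name from the session-level overall score.
5. Record and explain the departure from protocol 9.4.6.3 in SAP section 7. SAP 6.5 indicates that the primary analysis was already complete, and protocol 9.4 makes that an unblinded snapshot. If the change enters this SAP version, label it as made after the primary analysis.

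Cost: SAP wording and a little more analysis work, since all the scores are already scheduled. Participants without a Visit 1 score need a missing-covariate rule, and the result for early discontinuers will depend on the rule chosen.
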